8.7. Pregnancy Testing and Additional Evaluations

Women of childbearing potential must have negative urine or serum pregnancy test results at times specified in the Schedule of Activities (Section 5.8). Follicle stimulating hormone (FSH) may be determined as necessary to confirm postmenopausal status. Serum pregnancy tests and FSH will be performed at the central lab. The central lab will provide the urine pregnancy test kits to be used at the site.

At screening, coagulation profile (PT/INR) will be determined.

8.9. Serious Adverse Event Definitions

An SAE is any AE, occurring at any study drug dose and regardless of causality, with any of the following outcomes:

- Death
- Life-threatening
 - The term ‘life-threatening’ refers to an event in which the subject was at immediate risk of death from the reaction as it occurred. It does not include a reaction which hypothetically might have caused death had it occurred in a more severe form.
- Inpatient hospitalization or prolongation of existing hospitalization
 - “Hospitalization” means that the subject has been admitted to a hospital or emergency facility for observation and/or treatment that would not have been appropriate in a physician’s office or outpatient setting. Hospital admissions or surgery planned before any study drug is administered are not to be considered AEs unless there is unexpected deterioration of the subject’s condition after study drug treatment (eg, surgery must be performed earlier than planned).
- Complications occurring during hospitalization are AEs. If a complication prolongs hospitalization or fulfills any other criteria for seriousness, the complication becomes an SAE.

- If there is doubt whether hospitalization occurred or was necessary, the associated AE should be considered serious.
- Hospitalization for elective treatment of a pre-existing condition that has not worsened is not considered to be an AE.
- Persistent or significant disability/incapacity
 - Disability/incapacity is defined as substantial disruption of a person's ability to perform normal life functions. This definition is not intended to include events of relatively minor medical significance, such as uncomplicated headache, nausea, vomiting, influenza, or accidental trauma, which may interfere with or prevent normal life functions but are not substantial disruptions.
- Congenital anomaly/birth defect
- Important medical event
 - Medical or scientific judgment should be exercised in deciding whether SAE reporting is appropriate in other situations. An important medical event is an event that may not result in death, be life-threatening, or require hospitalization, but that may be considered an SAE when, based on appropriate medical judgment, it may jeopardize the subject and may require medical or surgical intervention to prevent one of the outcomes listed above. Examples of such medical events include allergic bronchospasm requiring intensive treatment in an emergency facility or at home, blood dyscrasias or convulsions that do not result in inpatient hospitalization, or the development of drug dependency or drug abuse.

An SAE requires additional detailed reports and follow-up. Detailed reports must address the Investigator's estimate of causality and whether or not the AE is identified in nature, severity, and frequency in the [Investigator's Brochure](#) or in other risk information that has been supplied to the Investigator (expectedness). SAEs must be recorded on the appropriate CRF page.

The terms "serious" and "severe" are not synonymous.

- The term "severe" is used to describe the severity of a specific event (such as a mild, moderate, or severe myocardial infarction); the event itself, however, may be of relatively minor medical significance (such as a severe headache). This is not the same as "serious," which is based on the criteria above and is usually associated with events that threaten a subject's life or functioning.
- A severe AE is not always considered serious in a clinical study. An event is considered serious when it meets at least one of the definitions above. For example, nausea lasting several hours may be considered severe but not an SAE. However, a stroke resulting in only minor disability may be considered mild, but would be considered an SAE based on the criteria above.
- Seriousness, not severity, is a guide for defining regulatory reporting obligations.

8.10. Procedures for Recording and Reporting Adverse Events and Serious Adverse Events Recording AEs and SAEs

All AEs spontaneously reported by subjects and/or reported in response to an open question from study personnel, or revealed by observation, physical examination, or other diagnostic procedure, will be recorded on the appropriate CRF. For both serious and non-serious AEs, the Investigator must determine, based on clinical judgment, both the severity of the events and their relationship to study treatment. All Grade 3 or 4 QTcF prolongations (average of triplicate ECG determination by central reading) must be reported to the Sponsor with the investigator's assessment of seriousness, causality, and a detailed narrative. These events, regardless of seriousness, should be reported within 24 hours of Investigator's awareness of the event.

When an AE or SAE occurs, it is the Investigator's responsibility to review all documentation relevant to the event (eg, hospital progress notes; laboratory and diagnostic reports). The Investigator will then record all relevant information regarding the event on the appropriate CRF. All AEs and SAEs must be recorded, regardless of their relationship to study treatment. It is not acceptable for the Investigator to send photocopies of the subject's medical records to the Sponsor in place of proper CRF completion. However, there may be instances when copies of medical records are requested. In such instances, all information identifying the subject will be redacted before their submission.

The Investigator will also attempt to establish a diagnosis of the event based on signs, symptoms, and/or other clinical information. In such cases, the diagnosis, and not the signs or symptoms, should be documented as the AE or SAE.

8.10.1. Disease-specific AEs and SAEs

Disease progression/worsening of AML should not be recorded as an adverse event. However, events associated with disease progression, such as thrombocytopenia, may be recorded as AE.

Death due to disease progression should not be recorded as adverse event or serious adverse event and should be recorded on the outcomes case report form (CRF).

8.10.2. Assessment of Severity

The Investigator must determine the severity of both serious and non-serious AEs, based on clinical judgment. The severity of each AE, including any abnormal laboratory test result, will be determined using CTCAE v4.03. When CTCAE v4.03 criteria do not apply, severity will be defined according to the following criteria:

Mild	The event, sign, and/or symptom is easily tolerated by the subject, causing minimal discomfort and not interfering with normal daily activities (Grade 1)
Moderate	The event causes sufficient discomfort to interfere with normal daily activities (Grade 2)
Severe	The event prevents the subject from performing normal daily activities (Grade 3)

Life-threatening	The event places the subject at immediate risk of death (Grade 4)
Death	The event results in the subject's death (Grade 5)

8.10.3. Assessment of Causality

The Investigator must determine the relationship of each AE and SAE to study treatment. The Investigator will use clinical judgment to determine this relationship. Other causes, such as concurrent medication or illness, other risk factors, and the event's temporal relationship to study treatment, will be considered. The Investigator will also consult the Investigator's Brochure and/or other product labeling information provided by the Sponsor.

There may be situations when an SAE occurs with minimal information for the initial report. However, it is very important that the Investigator assess causality of every SAE before reporting the event. The Investigator may change his or her opinion of causality in light of follow-up information and amend the SAE report. The causality assessment is one of the most important items for regulatory reporting and should not be left undone.

Relationship of an AE or SAE to study treatment will be defined according to the following criteria:

Definite	There is a clear temporal relationship to study treatment, with no other possible cause.
Possible	A temporal relationship to study treatment is not clear, and alternative etiologies are possible.
Not Related	There is no temporal relationship to study treatment, and/or there is evidence of an alternative cause such as a concurrent medication or illness.

All unexpected events are events that are not identified in the [Investigator's Brochure](#).

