5.6.4.3. Quizartinib Dose Escalation Rules and Definitions

CYCLE 1 DAY 16

For subjects not taking a strong CYP3A4 inhibitor the dose of quizartinib will be increased to 60 mg/day starting on Day 16 if the subject's average QTcF (QT interval corrected with Fridericia's formula), based on triplicate reading, is ≤ 450 msec on and before Day 15.

For subjects taking a strong CYP3A4 inhibitor, the dose of quizartinib will be increased to 30 mg/day providing they meet the above QTcF requirements.

CYCLE 2 DAY 1

Subjects who fail to achieve a CR, CRp or CRi as defined in Section 7.2 after at least one 28-day cycle of therapy, and may undergo dose escalation providing the following criteria are met:

- The subject has not had a Grade 3 or higher, non-hematologic, and related adverse event.
- No increase in QTcF more than 60 msec above baseline.

- The subject must not have aplastic bone marrow at the time of the proposed dose escalation.

In addition, subjects who achieved a response (CR, CRi, CRp, or PR) at any time and who subsequently relapsed may undergo dose escalation provided they meet the same criteria as above.

For subjects not taking a strong CYP3A4 inhibitor the dose of quizartinib will be increased to 60 mg/day.

For subjects taking a strong CYP3A4 inhibitor, the dose of quizartinib will be increased to 30 mg/day providing they meet the above requirements.

Following dose escalation, triplicate ECG determinations should be performed at least once weekly for 2 weeks to monitor QTcF prolongation.

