5.6.4.4. Quizartinib Dose Reduction Rules and Definitions

The dose of quizartinib will be reduced stepwise from 60 mg/day to 30 mg/day or from 30 mg/day to 20 mg/day, based on the following criteria:

QTcF (QT interval corrected with Fridericia's formula) Prolongation

- Grade 2 (QTcF average of triplicate readings > 480 msec)
 - The dose will be reduced without interruption.
 - If 20 mg/day is the current dose, dosing will be interrupted for up to 14 days. If QTcF returns to within 30 msec of baseline or ≤ 450 msec within 14 days, treatment may be resumed at 20 mg/day.
- Grade 3 (QTcF average of triplicate readings > 500 msec)
 - Dosing will be interrupted for up to 14 days. If QTcF returns to within 30 msec of baseline or ≤ 450 msec within 14 days, treatment may be resumed at a reduced dose.
 - If 20 mg/day is the current dose, dosing will be interrupted for up to 14 days. If QTcF returns to within 30 msec of baseline or ≤ 450 msec within 14 days, treatment may be resumed at 20 mg/day. If Grade 3 event returns, treatment will be discontinued.
- Grade 4 (QTcF >500 msec or >60 msec change from baseline, and Torsade de pointes or polymorphic ventricular tachycardia or signs/symptoms of serious arrhythmia)
 - Treatment will be discontinued.

See Section 8.5 for clinical guidelines for the management of QT prolongation.

Non-hematologic Toxicity

Grade 3 or 4 related to quizartinib and persisting >48 hours without improvement to \leq Grade 2.

- Dosing will be interrupted for up to 14 days.

- If toxicity improves to \leq Grade 1 within 14 days, treatment may be resumed at the reduced dose.

Myelosuppression

In a subject with CRp or CRi, the dose may be reduced at the Investigator's discretion if:

- The subject has been treated for a minimum of 2 cycles.
- Platelet count is $<100 \times 10^9/L$ and ANC is $\leq 1000 \times 10^9/L$.
- Marrow blast count is $<5\%$.
- There is no evidence of extramedullary disease.

Initiation of concomitant treatment with a strong CYP3A4 inhibitor is identified in [Appendix 1: List of Potential QT Prolonging Drugs, CYP3A4 Inhibitors/Inducers, and P-glycoprotein Inhibitors/Inducers](#).

The dose will be reduced one level (60 mg to 30 mg or 30 mg to 20 mg) when treatment with a strong CYP3A4 inhibitor is initiated.

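### The causality categories in section 8.10.3 are neither exhaustive nor mutually exclusive, so some events fit no category and clearer timing can give a weaker rating

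*Combined protocol and SAP*

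**What the plan says.** Section 8.10.3 makes the scale the definition of relatedness: "Relationship of an AE or SAE to study treatment will be defined according to the following criteria". There are three categories:

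- *Definite* is the strictest: the timing must be clear and nothing else may be a candidate cause.
- *Possible* sits in the middle, with the wording "A temporal relationship to study treatment is not clear, and alternative etiologies are possible".
- *Not Related* is the widest, since either of its two limbs is enough: "There is no temporal relationship to study treatment, and/or there is evidence of an alternative cause such as a concurrent medication or illness".

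The same section asks for judgment: "The Investigator will use clinical judgment to determine this relationship". It tells the investigator to weigh other causes, timing and the Investigator's Brochure, and lets an SAE's causality be amended on follow-up.

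Relatedness is a condition in several provisions. The non-hematologic toxicity rule in section 5.6.4.4 (also in the synopsis) applies to toxicity that is "Grade 3 or 4 related to quizartinib and persisting" beyond a stated time. One Cycle 2 Day 1 escalation criterion in section 5.6.4.3 reads "The subject has not had a Grade 3 or higher, non-hematologic, and related adverse event". Section 5.4.5 requires withdrawal of treatment for an intolerable AE that is related. Section 8.10.4 lists causal relationship among the minimum information for an SAE. The documents do not say whether *Possible* counts as related.

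**The concern.** A causality scale should place every event in one category, and stronger evidence of a drug effect should never lower the rating. This scale does neither. The event that it handles worst is one that starts on treatment with clear timing and also has another candidate explanation.

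The protocol gives reason to expect such events. Section 3.3 ties hematologic toxicity to the underlying disease and also attributes continued neutrophil and platelet suppression to quizartinib. The *Not Related* wording names concurrent illness and medication as alternative causes. All subjects have relapsed or refractory leukemia, and section 5.6.6.1 allows QT-prolonging drugs judged essential.

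At stake are the validity and comparability of causality ratings across about 150 open-label centers, and whether provisions conditioned on relatedness are reached for the events they were written for.

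**Working it through.** The plan gives no figure to reproduce; this is a check of logic. The inputs are the three definitions in section 8.10.3.

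**Step 1. Set out the combinations.** The definitions use two attributes. Timing can be clear, not clear or absent. An alternative cause can be absent, possible without evidence, or supported by evidence. I take evidence of an alternative to imply that an alternative is possible, and an unclear link to differ from no link. That gives 3 × 3 = 9 combinations.

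**Step 2. Apply the definitions as written.**

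| Temporal link | No alternative | Alternative possible, no evidence | Evidence of alternative |
|---|---|---|---|
| Clear | Definite | **No category** | Not Related |
| Not clear | **No category** | Possible | **Possible and Not Related** |
| None | Not Related | Not Related | Not Related |

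**Step 3. Count.** Six combinations fit exactly one category, two fit none and one fits two: 6 + 2 + 1 = 9. The two empty cells show that the scale is not exhaustive; the double cell shows that it is not exclusive.

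**Step 4. Check the ordering.** In the right-hand column, an event with a clear link is *Not Related*, while one with an unclear link and the same evidence may be called *Possible*. Better timing can therefore produce a weaker rating. The cause is the and/or, which makes evidence of an alternative sufficient whatever the timing.

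**Step 5. Vary the reading.** If an unclear link is taken to include no link, the cells for no link with a possible or evidenced alternative also meet *Possible*. The count becomes four single, two empty and three double: 4 + 2 + 3 = 9. The two gaps and the reversed ordering remain.

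**Step 6. See what depends on the rating.**

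- Conditioned on relatedness: the non-hematologic toxicity rule (5.6.4.4), the Cycle 2 Day 1 escalation criterion (5.6.4.3) and one mandatory withdrawal reason (5.4.5).
- Not conditioned on it: recording of all AEs and SAEs (8.10), reporting of all SAEs and deaths and of QTcF prolongation of Grade 3 or higher (8.10.4), the QTcF dose rules (5.6.4.4 and 8.5), Day 16 escalation (5.6.4.3) and withdrawal on the investigator's opinion (5.4.5).

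**The case against.** The strongest reply is that section 8.10.3 calls for clinical judgment, so no investigator would apply the wording mechanically. That carries some weight: misclassification is a risk when the text is followed, not a demonstrated result. But the judgment must still be recorded in one of three categories, and for two combinations none fits. Sites must then improvise, and may do so differently.

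The second reply is that many safeguards do not use relatedness, as listed above. That also stands. It limits the harm, but those safeguards capture events without correcting the rating, and they do not replace the relatedness condition where one is written.

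A reader might go further and infer any of four things, none of which the documents support:

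- *Every event with a possible alternative becomes Not Related.* That category requires evidence of the alternative; a mere possibility leaves an event with clear timing unclassified.
- *The dose rules are disabled.* They still operate for events rated *Definite*, and for *Possible* if that counts as related.
- *Tables of related events will be too low.* The synopsis and section 13.8 plan summaries of treatment-emergent events and specify no related-event table.
- *The error runs in one direction.* Unclassifiable events have no determined direction, and the double cell can be rated either way.

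**Conclusion.** The point holds as a defect in a stated definition. As written, the scale has two gaps, one overlap and one reversal of order. Drug-related events may be misclassified as *Not Related* or rated inconsistently across sites, and provisions that require a related event may not be triggered for them.

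The size cannot be computed, because the documents do not give the share of events that have both a temporal link and an alternative cause. The finding rests on the wording alone and on the two reading assumptions in the check; changing the second makes the overlap larger. The primary and secondary efficacy analyses are untouched. The defect should be corrected, but the safeguards that do not depend on relatedness limit its reach.

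**What to change.** Reword the table in section 8.10.3 so that each event has exactly one category:

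- *Definite*: a clear temporal link and no other possible cause (unchanged in substance).
- *Not Related*: no reasonable temporal relationship, or an alternative cause that clearly explains the event. Delete the and/or limb that rests on evidence alone.
- *Possible*: every other event. This includes a clear or reasonable link with alternatives also possible, and an unclear link with no alternative.

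The first two cannot both be true of one event, and the third is their complement, so the scale is exhaustive and exclusive by construction. Splitting evidenced alternatives into those that clearly explain the event and those that do not gives 3 × 4 = 12 combinations: 1 *Definite*, 5 *Possible* and 6 *Not Related*, with no gap or overlap. An unclear link is again treated as distinct from no reasonable link. Clearer timing then never lowers the rating.

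The sponsor should also state which categories count as related, and reconcile that statement with sections 5.4.5, 5.6.4.3 and 5.6.4.4 and the synopsis. The Cycle 2 Day 1 escalation criterion needs reconciling in its own right: the synopsis refers to a dose interruption or reduction for a related Grade 3 or higher non-hematologic event, whereas section 5.6.4.3 refers to having had such an event. Which rule is intended is for the sponsor to settle.

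The cost is two reworded table cells, a sentence on what counts as related, revised CRF guidance and re-review of any events already coded. The count of related events will probably rise.

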8.10.4. SAE Reporting

Every SAE occurring during the study, as defined above, must be reported by the Investigator to the Sponsor's designated contact as soon as possible, but no later than within 1 working day from the time when the Investigator becomes aware of the SAE. All SAEs and deaths must be reported, whether or not they are considered to be causally related to study treatment. SAE reporting forms will be provided to each study site. Additionally, QTcF prolongation \geq Grade 3, either serious or non-serious and whether or not causally related must be reported by the Investigator within 24 hours of awareness. The information recorded on these forms will include at least the following:

- Subject number
- Identity of the event
- Study drug name and dose

- Narrative of the event
- Investigator's assessment of the event's severity and relationship to study treatment
- Investigator's name and signature

If serious, unexpected adverse drug reactions occur, the Sponsor will notify the appropriate regulatory agency or agencies and all participating Investigators on an expedited basis.

All SAEs will be monitored until they have resolved or are clearly determined to result from a chronic or intercurrent condition.

In the case of an SAE, the investigator must contact the Sponsor by telephone or fax immediately (within 24 hours of awareness). The investigator should complete and submit an SAE Worksheet containing all information that is required by the Regulatory Authorities to the Sponsor or designee by fax immediately (within 24 hours of awareness).

If the faxing of an SAE Worksheet is not possible or is not possible within 24 hours, the local drug safety contact should be informed by phone. For contact details see the Study Reference Manual for international number access. Please fax or email the SAE Worksheet to:

Novella Clinical Safety Management

US safety hotline: [REDACTED]

US fax number: [REDACTED]

E-mail: [REDACTED]

If there are any questions, or if clarification is needed regarding the SAE, please contact the Sponsor's Medical Monitor or designee (see contact details of key Sponsor's Personnel in the Study Reference Manual). Follow-up information for the event should be sent promptly (within 7 days) as necessary.

The Sponsor or Sponsor's designee will submit expedited safety reports (ie, IND Safety Reports) to the Regulatory Agencies (ie, FDA) as necessary, and will inform the investigators of such regulatory reports. Investigators must submit safety reports as required by their IRB /IEC within timelines set by regional regulations (ie, EU HAS, FDA). Documentation of the submission to and receipt by the IRB / IEC of expedited safety reports should be retained by the site.

The Investigator may contact the Sponsor's Medical Monitor for any other problem related to the safety, welfare, or rights of the study participant (subject/patient).

Full details of the SAE should also be recorded on the medical records and on the CRF.

The following minimum information is required:

- Study number
- Subject number, sex and age
- The date of report
- A description of the SAE (event, seriousness of the event)
- Causal relationship to the study drug

